- Treatment period (12 weeks)
- Post-treatment follow-up period (21 ± 3 days)

Eligible subjects from the previous double-blind trials will be eligible to roll over into this open-label extension trial. Overall, the trial duration from first ICF signed to the final subject assessment is expected to be several years.

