8.7.4 Electrocardiogram

Electrocardiograms will be performed at the time points described in the schedule of assessments (Table 1.3-1). Subjects should be monitored for potentially clinically significant ECG results ([Section 10.7](#)).

Electrocardiogram recordings will be obtained after the subject has been supine and at rest for at least 5 minutes. Additional ECGs may be obtained at the investigator's discretion and should always be obtained in the event of an ET. The principal investigator

(or qualified designee) will review, sign, and date each ECG reading, noting whether or not any abnormal results are of clinical significance. The ECG will be repeated if any results are considered to be clinically significant. A central ECG service will be used for reading all ECGs in order to standardize interpretations for the safety analysis.

Rollover subjects will be enrolled in trial based on the screening/baseline ECG results from the trial site. If at screening/baseline, according to the investigator's judgment, any abnormal ECG finding is deemed medically significant (impacting the safety of the subject or the interpretation of the trial results), the subject should be excluded from the trial. Abnormal results for ECGs should be repeated once at screening/baseline with 3 consecutive ECG recordings to ensure reproducibility of the abnormality before excluding a subject based on the criteria noted above. Each ECG recording should be taken approximately 5 minutes apart (the ECG result reported will be evaluated at each time point). The central ECG service will provide the corrections for the 3 ECGs performed. If the screening/baseline ECG results from the central reader, when available, indicate a QTcF \geq 450 msec in men and \geq 470 msec in women (unless due to ventricular pacing at screening/baseline), the investigator must contact the medical monitor to discuss the subject's continued participation in the trial.

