10.7 Appendix 7: Criteria for Identifying ECG Measurements of Potential Clinical Relevance

Variable	Criterion Value ^a	Change Relative to Baseline ^a
Rate		
Tachycardia	≥ 120 bpm	increase of ≥ 15 bpm
Bradycardia	≤ 50 bpm	decrease of ≥ 15 bpm
Rhythm		
Sinus tachycardia ^b	≥ 120 bpm	increase of ≥ 15 bpm
Sinus bradycardia ^c	≤ 50 bpm	decrease of ≥ 15 bpm
Supraventricular premature beat	all	not present → present
Ventricular premature beat	all	not present → present
Supraventricular tachycardia	all	not present → present
Ventricular tachycardia	all	not present → present
Atrial fibrillation	all	not present → present
Atrial flutter	all	not present → present
Conduction		
1 atrioventricular block	PR ≥ 200 msec	increase of ≥ 50 msec
2 atrioventricular block	all	not present → present
3 atrioventricular block	all	not present → present
Left bundle-branch block	all	not present → present
Right bundle-branch block	all	not present → present
Pre-excitation syndrome	all	not present → present
Other intraventricular conduction block ^d	QRS ≥ 120 msec	increase of ≥ 20 msec
Infarction		
Acute or subacute	all	not present → present
Old	all	not present → present
		≥ 12 weeks post trial entry
ST/T Morphological		
Myocardial ischemia	all	not present → present
Symmetrical T-wave inversion	all	not present → present
Increase in QTc	QTcF > 450 msec (males) QTcF > 470 msec (females)	

QTc = corrected QT interval; QTcF = QT interval corrected for heart rate using Fridericia's formula.

^aIn order to be identified as potentially clinically relevant, an on-treatment value must meet the "Criterion Value" and also represent a change from the subject's baseline value of at least the magnitude shown in the "Change Relative to Baseline" column.

^bNo current diagnosis of supraventricular tachycardia, ventricular tachycardia, atrial fibrillation, atrial flutter, or other rhythm abnormality.

^cNo current diagnosis of atrial fibrillation, atrial flutter, or other rhythm abnormality.

^dNo current diagnosis of left bundle branch or right bundle branch block.

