9.3 Physical Examination and Vital Signs

Summary statistics for changes from baseline in vital signs will be provided for the Safety Sample. By-patient listings will be provided for physical examination.

Potentially clinically relevant vital signs measurements identified in the open-label treatment phase for the Safety Sample will be listed and summarized. Criteria for identifying vital signs of potential clinical relevance are provided in [Appendix 1](#).

In addition, the change from baseline in weight, BMI, and waist circumference, and potentially clinically relevant abnormalities in weight, will also be summarized.

9.4 12-Lead ECG

Summary statistics and incidence of potentially clinically relevant changes will be provided for ECG parameters.

For the analysis of QT and QTc, data from three consecutive complexes (representing three consecutive heart beats) will be measured to determine average values. The following QT corrections will be used for reporting purposes in the clinical study report:

- 1) QTcB is the length of the QT interval corrected for heart rate by the Bazett formula:

$$\text{QTcB} = \text{QT}/(\text{RR})^{0.5}$$
 and
- 2) QTcF is the length of the QT interval corrected for heart rate by the Fridericia formula:

$$\text{QTcF} = \text{QT}/(\text{RR})^{0.33}$$
- 3) QTcN is the length of the QT interval corrected for heart rate by the FDA Neuropharm Division formula:
$$\text{QTcN} = \text{QT}/(\text{RR})^{0.37}$$

Potentially clinically relevant changes in the 12-lead ECG identified in the open-label treatment phase for the Safety Sample will be listed and summarized by treatment group. Criteria for identifying ECG measurements of potential clinical relevance are provided in [Appendix 3](#).

Categorical changes in ECG parameters during the open-label treatment phase will be summarized based on the following criteria:

Categorical Change Criteria in QT/QTc Parameters		
Classification	Category	Criteria
QT	New Onset (> 450 Msec)	New onset (>450 msec) in QT means a subject who attains a value > 450 msec during treatment period but not at baseline.
QTc *	New Onset (\geq 450 Msec for men and \geq 470 Msec for women)	New onset (\geq 450 Msec for men and (\geq 470 Msec for women) in QTc means a subject who attains a value \geq 450 Msec for men or \geq 470 Msec for women during treatment period but not at baseline.

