10.1 Study Visit Windows

Study visit windows will be used to map visits using study day intervals. Observations at each scheduled visit and Early Termination will be assigned to Week 2, Week 4, Week 8 and Week 12 visits based on their visit windows as shown in [Table 10.1A](#). This visit window convention applies to tables and listings for all efficacy and safety scales (CC1 [REDACTED])

CCI

SAS, AIMS and BARS). This derived study window variable will be named as DAY and will be footnoted. In listings, it will be listed along with the CRF study visit.

Table 10.1A shows classifications for study day intervals in the open-label treatment phase. The variable “target day” is defined using the number of days since the start of open-label brexpiprazole dosing. The first day of open-label brexpiprazole dosing is defined as “Day 1”.

If more than one observation falls within a particular study day interval, then the last observation within that interval is used. Evaluations occurring more than 7 days after the last open-label brexpiprazole dosing date will not be mapped into study visit windows, and will be excluded from the analysis.

Table 10.1A: Study Day and Visit Windows in the Open-label Treatment Phase

Week	Target Day ^a	Study Day Interval ^a
2	14	2-21
4	28	22-42
8	56	43-70
12	84	71-91 ^b

^a Relative to the first day of open-label brexpiprazole in the open-label treatment phase.

^b Evaluations occurring more than seven days after the last dosing date of open-label brexpiprazole in the open-label treatment phase will be excluded from the efficacy analyses.

[figure not shown]

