Appendix 3**Criteria for Identifying ECG Measurements of Potential Clinical****Relevance**

Variable	Criterion Value ^a	Change Relative to Baseline ^a
Rate		
Tachycardia	≥ 120 bpm	increase of ≥ 15 bpm
Bradycardia	≤ 50 bpm	decrease of ≥ 15 bpm
Rhythm		
Sinus tachycardia ^b	≥ 120 bpm	increase of ≥ 15 bpm
Sinus bradycardia ^c	≤ 50 bpm	decrease of ≥ 15 bpm
Supraventricular premature beat	all	not present → present
Ventricular premature beat	all	not present → present
Supraventricular tachycardia	all	not present → present
Ventricular tachycardia	all	not present → present
Atrial fibrillation	all	not present → present
Atrial flutter	all	not present → present
Conduction		
1° atrioventricular block	PR ≥ 200 msec	increase of ≥ 50 msec
2° atrioventricular block	all	not present → present
3° atrioventricular block	all	not present → present
Left bundle-branch block	all	not present → present
Right bundle-branch block	all	not present → present
Pre-excitation syndrome	all	not present → present
Other intraventricular conduction block ^d	QRS ≥ 120 msec	increase of ≥ 20 msec
Infarction		
Acute or subacute	all	not present → present
Old	all	not present → present
		≥ 12 weeks post study entry
ST/T Morphological		
Myocardial Ischemia	all	not present → present
Symmetrical T-wave inversion	all	not present → present
Increase in QTc	QTcF ≥ 450 msec (men) QTcF ≥ 470 msec (women)	

^a In order to be identified as potentially clinically relevant, an on-treatment value must meet the “Criterion Value” and also represent a change from the subject’s baseline value of at least the magnitude shown in the “Change Relative to Baseline” column.

^b No current diagnosis of supraventricular tachycardia, ventricular tachycardia, atrial fibrillation, atrial flutter, or other rhythm abnormality.

^c No current diagnosis of atrial fibrillation, atrial flutter, or other rhythm abnormality.

^d No current diagnosis of left bundle branch block or right bundle branch block.

12 Proposed List of Summary Tables

- CT-1.1 Subject Disposition (Enrolled Sample)
- CT-1.2 Subject Disposition by Center (Enrolled Sample)
- CT-1.3 Subject Completion Rates by Week (Enrolled Sample)
- CT-1.4 Enrollment by Country (Enrolled Sample)
- CT-1.5 Enrollment by Country by Age Group (Enrolled Sample)
- CT-1.6 Summary of Proportion of the Face-to-Face and Virtual Visits by Study Week (Enrolled Sample)
- CT-2 Reasons for Discontinuation (Enrolled Sample)
- CT-3.1 Demographic Characteristics (Enrolled Sample)

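### The 12-week condition on a new 'Old' infarction does not fit an ECG schedule whose only planned post-baseline recording is at Week 12 ± 3 days or early termination (minor)

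*SAP*

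**What the plan says.** In SAP Appendix 3 the 'Old' infarction row requires a pattern absent at baseline and present later, followed by "≥ 12 weeks post study entry". Protocol Appendix 7 carries the same row with "≥ 12 weeks post trial entry". Footnote a in both tables makes the change column binding: an on-treatment value must meet the criterion and "also represent a change from the subject’s baseline value of at least the magnitude shown". No other row in the table has a time condition. The adjacent 'Acute or subacute' row asks only that the finding be new. Neither document says what date counts as study or trial entry.

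Protocol Table 1.3-1 schedules ECGs at screening/baseline and at Week 12 or early termination (ET), with a ± 3 day window on treatment visits. None is scheduled at the 21-day follow-up. Protocol 8.7.4 allows further ECGs at the investigator's discretion and says that they "should always be obtained in the event of an ET". On reporting, SAP 9.4 states: "Potentially clinically relevant changes in the 12-lead ECG identified in the open-label treatment phase for the Safety Sample will be listed and summarized". The outputs are CT-12.2.1 (listing) and CT-12.2.2 (incidence).

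**The concern.** The time threshold equals the full planned treatment length, and the one scheduled post-baseline ECG sits on that threshold or before it. A subject with a clean baseline who stops midway, and whose ET tracing shows a pattern read as old, is not flagged. Two completers with the same finding, one seen on Day 81 and one on Day 87, can be classified differently because of appointment dates alone.

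ECG change is a secondary safety endpoint (Protocol Table 3-1). A zero in the 'Old' row could come from the rule rather than from the data, and a reader of the table could not tell which. With entry undefined, two programmers following the SAP could also place the cut-off on different days.

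**Working it through.** The plan gives no figure on this point to reproduce, so the check is date arithmetic.

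**Inputs from the documents**
- Condition: at least 12 weeks, that is 12 × 7 = 84 days, after entry (SAP Appendix 3, Protocol Appendix 7).
- Day 1 is the first open-label dose, and the Week 12 target is Day 84 (SAP 10.1).
- Visit window ± 3 days (Protocol Table 1.3-1), giving Days 81-87.
- Gap g in days from entry to first dose. Protocol 6.1 and SAP 3.2 place the first dose one day after the last double-blind dose, which is expected on the screening/baseline visit day (g = 1). The same sections also say that the starting dose is received at the screening/baseline visit (g = 0); these statements need reconciling. A gap of up to 3 days may be permitted (g = 3).
- Delayed-entry subjects have a separate screening visit, with a screening period of up to 21 days that may be extended (SAP 3.1).

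**Formula.** Days since entry on study Day n = n − 1 + g. The condition is met when n − 1 + g ≥ 84, that is n ≥ 85 − g.

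| Entry to first dose | Days since entry over Days 81-87 | Window days that fail |
|---|---|---|
| g = 0 | 80-86 | Days 81-84 (4 of 7) |
| g = 1 | 81-87 | Days 81-83 (3 of 7) |
| g = 3 | 83-89 | Day 81 (1 of 7) |
| g = 21 (delayed entry, dated from screening) | 101-107 | none |

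With g = 0 even an on-target Day 84 visit fails, at 83 days. With g = 21 the cut-off is Day 64, so a late ET ECG would also qualify. A delayed-entry subject whose entry is dated from the baseline visit is dosed that day and falls under g = 0.

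**Share of rollover subjects who cannot meet the condition at their last scheduled ECG.** This needs two quantities that the documents do not give. I assume an early-termination share d of 0 to 40%, with every ET ECG before the cut-off. For completers I take either an even spread over Days 81-87 or a spread peaked at Day 84 (weights 1, 2, 3, 4, 3, 2, 1; total 16). With f the share of completers who fail, the overall share is d + (1 − d) × f.

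- g = 1, even: f = 3/7 = 43%; overall 43% to 0.4 + 0.6 × 0.429 = 66%.
- g = 1, peaked: f = 6/16 = 38%; overall 38% to 0.4 + 0.6 × 0.375 = 63%.
- g = 0, even: f = 4/7 = 57%; overall 57% to 0.4 + 0.6 × 0.571 = 74%.
- g = 0, peaked: f = 10/16 = 63%; overall 63% to 0.4 + 0.6 × 0.625 = 78%.
- g = 3, even: f = 1/7 = 14%; overall 14% to 0.4 + 0.6 × 0.143 = 49%.
- g = 1, every completer seen on Day 84 or later: f = 0; overall 0 to 40%, the early terminators only.

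These are shares of subjects whose scheduled ECG could not trigger the flag. They are not shares of infarctions missed.

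**The case against.** The best defence is that the condition has a purpose. A pattern already read as old soon after entry may predate open-label treatment and have been overlooked on the baseline tracing, so a delay guards against calling it new. That stands as a reason to want specificity. It does not make the threshold workable here, because there is no routine later ECG at which the finding could be picked up. The requirement of absence at baseline already provides the main comparison.

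The effect is also limited. The investigator reviews and signs each ECG, a central service reads all of them, and an event judged to be an adverse event enters the adverse event tables. All of that stands: the gap concerns the planned flag, not detection.

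Three stronger conclusions are tempting and are not supported.
- A reader might infer that most subjects are excluded. That depends on dropout, on visit timing and on what counts as entry; the range above runs from 0 to 78%.
- A reader might infer that those who stop early can never be flagged. Unscheduled ECGs are allowed, and a delayed-entry subject could qualify at a late ET visit if entry is dated from screening. Unscheduled ECGs help little in practice: before the cut-off they fail too, and well after it the subject is past planned treatment.
- A reader might infer that new infarctions go unreported. The 'Acute or subacute' row has no time condition, and neither do the ischemia and T-wave inversion rows, so only a pattern read solely as 'Old' is affected.

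**Conclusion.** The concern holds, as a minor defect. As written, the 'Old' row leaves out new patterns on ET ECGs taken before 12 weeks and on rollover completers' Week 12 ECGs taken early in the permitted window: Days 81-83 with dosing one day after entry, Days 81-84 with dosing on the entry day. It also rests on an undefined entry date. This is a rule that does not match the trial's own schedule, and not merely a missing detail. The two documents agree on the criterion; the mismatch is between that criterion and the ECG schedule.

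The window days follow from the documents once g is fixed. Any percentage of subjects rests on the assumed dropout and visit spread and should be read only as a range. Consequences are confined to one row of a descriptive incidence table and its listing.

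**What to change.** In SAP Appendix 3, with a matching clarification to Protocol Appendix 7, remove the 12-week condition from the 'Old' infarction row for this trial. Every 'Old' pattern absent at baseline and present at an on-treatment or Week 12/ET ECG is then listed in CT-12.2.1 and counted in CT-12.2.2, with study day and the baseline reading shown in the listing.

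If the sponsor prefers to keep the condition for specificity, define study entry (including for delayed-entry subjects). Still report every new 'Old' pattern, and mark in the listing and table which cases meet the condition.

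The cost is one line in the SAP and one in the protocol, with no new data or procedures. The downside is that an old pattern missed on the baseline reading may occasionally be counted as new; study day and the baseline reading in the listing help to identify such cases.
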